Appendix L

Examples of Estimating Blood Loss

Zuckerwise. Estimated Obstetric Blood Loss With Visual Aid. *Obstet Gynecol* 2014.

Delivering providers will also adhere to NAVMEDWESTINST 6320.20, which specifies that once an EBL reaches 500cc, the delivering provider will move from an *estimation* of blood loss to utilizing a *quantitative* blood loss (QBL). QBLs are obtained by the weighing of chux pads, drapes, and linens that have been soiled (after first calibrating the scale to remove the original weight of the contaminated product). It also includes the blood that has been collected in the suction canister in the operating room.

In instances when EBL is decided upon at delivery, and ongoing bleeding occurs after the provider has left the room (and is called back), a QBL should be obtained. The QBL should be added to the initial EBL for a *cumulative* blood loss (CBL).

Percent decrease in hematocrit (Hct) – The percent change of the patients' Hct obtained on admission from that obtained after delivery. A post-operative Hct is routinely obtained six hours following a cesarean delivery. A Hct is not routinely obtained for patients having a vaginal delivery unless EBL exceeds 500cc. A post vaginal delivery Hct will not be obtained in patients for the sole purpose of this research study.

Rates of blood transfusion – The number of patients requiring blood transfusion divided by the total number of deliveries.

The types and amounts of products transfused – in patients requiring transfusion, the type of product (i.e, packed red blood cells, whole blood, fresh frozen plasma, platelets, and cryoprecipitate) will be recorded, along with how many of each type they received.

The use of uterotonic agents – in patients requiring uterotonic agents beyond the first bolus of oxytocin (i.e. second bolus of oxytocin, methylergonovine, 15-methyl Prostaglandin F_{2α}, misoprostol) will be recorded, along with how many doses of each

The need for surgical intervention – the number of patient's that require surgical intervention following a vaginal delivery for the purposes of controlling excessive blood loss divided by the total number of vaginal deliveries

The need for reoperation - the number of patients that require return to the operating room following a cesarean delivery for the purposes of controlling excessive blood loss divided by the total number of cesarean deliveries

Rates of hysterectomy – the number of patients requiring hysterectomy divided by the total number of deliveries

Admission to the Intensive Care Unit (ICU) - the number of patients requiring admission to the intensive care unit secondary to excessive blood loss divided by the total number of deliveries

Neonatal outcomes – incidence of fetal anemia, infection, hyperbilirubinemia, neurologic outcomes, and neonatal intensive unit admissions

Maternal mortality – incidence of mortality

Additionally, postpartum hemorrhage risk assessment will be utilized to stratify patients with regard to primary and secondary outcomes.

- Patients will be risk stratified to one of three risk categories depending on admission and intrapartum risk factors
 - High Risk Factors:
 - Placenta previa/ low lying placenta
 - Suspected accreta or percreta
 - Platelet count <70,000
 - Active bleeding
 - Known coagulopathy
 - Two or more medium risk factors
 - Medium Risk Factors:
 - Prior cesarean delivery, uterine surgery, or multiple laparotomies
 - Multiple gestation
 - > 4 prior births
 - Prior obstetric hemorrhage
 - Large myomas
 - EFW >4000
 - BMI > 40
 - Hct < 30%
 - Chorioamnionitis
 - >24 hours on Oxytocin
 - Magnesium sulfate
 - Low Risk: all patients not falling in the medium or high risk categories

Importance to Navy Medicine:

Beyond the potential impact that this study has in the reduction of maternal morbidity and mortality, it can also allow for perspective into resource management. Some of the Navy Military Treatment Facilities (MTFs) have limited blood bank stock, and massive hemorrhages requiring ongoing transfusion of products can quickly deplete the entirety of the supply. If we can find a solution that will reduce the number of instances where transfusion is necessary we can help to preserve limited resources. Likewise, this preventive measure will also have the potential to (cost) reduce the need for additional uterotonics, personnel, supplies and ICU beds.

There will be no collaboration with outside institutions.

Supplement A: TXA Protocol Administration (Modified from the NMCS Maternal Child Executive Committee's Policy)

1. TXA comes in a 1000 mg/10 mL vial. Nursing staff will pull this from the Pyxis at the same time they bring Oxytocin into the L&D room.
2. Add 1000 mg (or 1 vial) of 1000 mg/10 mL to 100 mL normal saline (100 mg/mL)
 - a. Bolus: 1 gram IV over 10 minutes
 - i. Set infusion pump rate to 600 mL/hr
3. Begin the TXA infusion directly following umbilical cord clamping for the intent of preventing postpartum hemorrhage.
 - a. The TXA may be run as a secondary line (i.e. is compatible with pitocin) per [name], Chairman of the Pharmacy Department
4. TXA should be administered in a separate IV line from blood products.
5. Two-person verification is required (this can be a second nurse or can be the physician or certified nurse midwife that is attending the delivery)
6. A single additional dose of TXA (1 gram IV over 10 minutes) can be repeated after 30 minutes if bleeding continues or if bleeding stops and then re-starts within 24 hours of the first dose (for a maximum dose of 2g in 24 hours). This additional dose is considered a treatment dose. This additional dose is not required by the study design, which is to assess TXA in the *prevention* of hemorrhage.

Supplement B: Patient Monitoring following delivery

1. After delivery patients will be observed on the Labor and Delivery floor for a minimum of one hour. Thereafter they will be transferred to the postpartum ward where they will be observed for a minimum of 24 hours.
2. The following physical assessments will be completed every 15 minutes x 1 hour , then every 30 min x 2 hours, then every 4 hours until discharge.
 - A. Vital signs: BP and pulse as above. Temperature Q1 hour (after 2 normal values will space to Q4 hours).
 - B. Fundal assessment: Placement and tone
 - C. Lochia assessment: Color, with or without clots, amount
 - D. Perineum assessment: Intactness (approximation of tissues/wound/lacerations), hematomas, swelling
 - E. Bladder assessment: Distention, voiding (noting/documentation of most recent void/amount, spontaneous/catheterization).
 - F. Any symptoms that the patient reports.
3. The nursing staff will immediately report any findings that are not within normal limits to the delivering provider or on-call provider:
 - A. BP systolic > 160 or < 100
 - B. BP diastolic > 90 or <50
 - C. Pulse > 100
 - D. Nausea, dizziness or SOB
 - E. Moderate to copious lochia
 - F. Increased swelling or pain in vagina or perineal/rectal area
 - G. Distended bladder not relieved by catheterization or patient voiding
 - H. Fundus displaced or above umbilicus (if differs from initial normal placement of uterus), unrelieved with empty bladder.
4. Documentation
 - A. All assessments are documented in Essentris. See below for notes needed:
 - B. Complete intake and output flow sheet
 - C. Complete Medication flow sheet
 - D. Complete the following computerized nursing notes:
 - E. Live Vaginal Delivery:
 1. OB MultiID Delivery Summary
 - F. Live C/Section:
 1. OB MultiID Delivery Summary

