9. WHO Recommendations for the Prevention and Treatment of Postpartum Haemorrhage. Geneva: World Health Organization; 2012.
10. WOMAN Trial Collaborators. Effect of early tranexamic acid administration on mortality, hysterectomy, and other morbidities in women with post-partum haemorrhage (WOMAN): an international, randomised, double-blind, placebo-controlled trial. Lancet. 2017 Apr 26.

Research Design:

a. General Approach: Prospective Cohort study

b. Description: Phase 4

c. Methods: One Arm

d. Statistical Analysis:

- SPSS software will be used for our statistical analysis. Normal distribution will be assumed given the intended number of patients for analysis. Categorical variables will be analyzed using the Chi-square test. The t-test will be utilized for the comparison of continuous interval data.

-Using postpartum hemorrhage rate of 2.86% (institutional data), and a desired impact of reducing the hemorrhage rates by 50% after implementation of the new protocol, then 890 subjects would need to be recruited to answer the question.

e. Safety Analysis Plan:

- Data collection for each participant will occur in real time during pre and post delivery times, therefore safety monitoring of the patient and data will be simultaneous.
- A Research monitor has been appointed to oversee the safe and ethical conduct of the study. Additionally, the Research Monitor will provide review and comment on any adverse events. The Research Monitor is not a member of the investigative team. The role of the Research Monitor is as follows:
 1. monitor the consent process to ensure an absence of coercion
 2. monitor data collection/clinical outcome
 3. review all adverse event reports with comments from the PI and forward to the IRB with his/her own comments. Adverse events must be received by the IRB within 5 business days of occurrence or reporting (within 24 hours for serious adverse events)
 4. ensure the inclusion/exclusion criteria are followed
 5. review data security measures
- Any emerging safety concerns to include any adverse event rate higher than this institution's historical average will result in a halt to the study.

Subject Population:

Pregnant women presenting for delivery at NMCSO

a. Exclusion/Inclusion criteria:

Exclusion:

- a. Age less than 18 years
- b. Planned cesarean hysterectomy
- c. Current anticoagulant use
- d. Subarachnoid hemorrhage
- e. Any active/current intravascular clotting (i.e. venous thromboembolic events)

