 2. For patients that present for delivery at a gestational age less than 34 weeks, it will be recommended that they discard their breast milk until 24 hours after their last TXA administration.
 3. Order TXA for patient in ESSENTRIS
 4. RN to pull TXA from Pyxis and put in patient's room
 5. TXA per protocol (see supplement A)
 6. The use of additional uterotonics or single additional dose of TXA is at the discretion of the delivering provider
 7. For patient monitoring protocol please see Supplement B.
 8. All neonates are monitored for a minimum of 24 hours either by the NICU or the Newborn Nursery. Vitals are taken every four hours. Weights and bilirubin levels are obtained daily. Daily physical exams are performed.
3. Data collection
 1. Participants will be assigned an individualized subject number upon their enrollment to the study.
 2. Participants will be followed from their enrollment into the study until six weeks postpartum.
 3. An Excel spreadsheet will be used to collect the variables as listed above.
 4. Once the variable collection is complete, the information will become de-identified.

5. Chart review will be performed to estimate institutional rates of the secondary outcomes in the 12 months preceding the initiation of the protocol.
4. Data Analysis
 1. SPSS software will be used for our statistical analysis. Normal distribution will be assumed given the intended number of patients for analysis. Categorical variables will be analyzed using the Chi-square test. The t-test will be utilized for the comparison of continuous interval data.
 2. Using a postpartum hemorrhage rate of 2.86% (institutional data), and a desired impact of reducing the hemorrhage rates by 50% after implementation of the new protocol, then 890 subjects would need to be recruited to answer the question.
 3. The secondary outcomes will also be tested against institutional rates. Institutional rates will be estimated by record sampling done at the time of data collection.

Experimental Procedures:

See supplement A

Research materials collected:

Variables to be collected:

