- Rare events from worldwide post marketing reports have included thromboembolic events (e.g., deep vein thrombosis, pulmonary embolism, cerebral thrombosis, acute renal cortical necrosis, and central retinal artery and vein obstruction), convulsion, chromatopsia, and visual impairment

Radiation/Laser Exposure: None

Justification/Minimization of Risks:

All identifiers will remain in the protected medical record. Any PHI extracted as a result of this study will be destroyed at the earliest opportunity consistent with conduct of the research, unless there is a health or research justification for retaining the identifiers or such retention is otherwise required by law. Protected health information will not be reused or disclosed to any other person or entity, except as required by law, for authorized oversight of the research study, or for other research for which the use or disclosure of protected health information would be permitted by approval of the IRB.

The current Maternal Child Executive Committee Policy on Tranexamic Acid (TXA) Administration will be followed to minimize any risks of harm to subjects.

Benefits:

Potential benefits of the research to the subject include a reduction in blood loss from delivery, decreased need for uterotonic medications, decreased need for blood transfusion, and less morbidity as a result of symptomatic anemia, resulting in increased satisfaction with the postpartum experience and increased maternal-neonate interactions.

Potential benefits of the research to the community/society included less overall maternal morbidity/mortality as well as a decreased demand on limited resources (i.e. blood products, uterotonic medications, time of additional healthcare providers, etc).

Requirements for Research Monitor:

Research Monitor Responsibilities:

Serves as a medical monitor, reviewing AEs as they are discovered to determine if the events suggest a trend toward increased risk to subjects that would require additional safeguards, subject notifications, or an invoking of stopping rules.

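### Whether hematocrit is measured after vaginal birth depends on blood loss that TXA is meant to reduce, so the comparison of hematocrit decrease among measured women is biased if TXA works, in a direction the documents do not fix

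*Combined protocol and SAP*

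**What the plan says.** The hematocrit entry under Secondary outcomes defines the percent change from the admission value to the post-delivery value, without restriction by mode of delivery. Availability then differs by mode. For cesareans, "A post-operative Hct is routinely obtained six hours following a cesarean delivery". For vaginal births, "A Hct is not routinely obtained for patients having a vaginal delivery unless EBL exceeds 500cc", and "A post vaginal delivery Hct will not be obtained in patients for the sole purpose of this research study".

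On treatment, Supplement A item 3 reads "Begin the TXA infusion directly following umbilical cord clamping for the intent of preventing postpartum hemorrhage", and the Benefits section says "Potential benefits of the research to the subject include a reduction in blood loss from delivery".

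On analysis, Study Procedures (Data Analysis, item 3) says "The secondary outcomes will also be tested against institutional rates". Data collection item 5 says "Chart review will be performed to estimate institutional rates of the secondary outcomes in the 12 months preceding the initiation of the protocol". Research Design (d) adds "The t-test will be utilized for the comparison of continuous interval data". A percent decrease is not a rate, so a t-test of study women against historic patients is the natural reading, but it is inferred. No sentence says what happens to women without a post-delivery Hct. The only stratification planned is by hemorrhage risk category. Mode of delivery is among the variables to be collected.

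**The concern.** Under the 500 cc rule, whether a vaginal birth contributes an Hct is decided after TXA has started, by a quantity TXA is meant to change. Women whom TXA keeps at or below 500 cc leave the measured set, so the measured women in the two periods are no longer alike. Applying the same rule to historic charts does not cure this, because the selection acts on a consequence of treatment.

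The Objectives name vaginal delivery as the setting where data are lacking. There, a null Hct result could be read as no benefit, or a positive one taken at face value, when the measurement rule produced part of either. If TXA does nothing and blood loss is judged alike in both periods, this mechanism creates no difference.

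**Working it through.** **The plan's own figure.** The documents give no figure for Hct. The 890 for the primary outcome reproduces as a one-sample comparison with a fixed rate. With p0 = 0.0286, p1 = 0.0143, two-sided 5% and 80% power (both assumed), n = [(1.96·√(p0(1−p0)) + 0.8416·√(p1(1−p1)))/(p0−p1)]² = 889.99. It does not involve Hct.

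**Vaginal births, strict 500 cc rule.** Blood loss in mL stands in for Hct (assumed). Loss is lognormal with median m = 300, 350 or 400 mL (assumed). The 2.86% is used as P(loss ≥ 1000 mL) in vaginal births. That is an assumption, since it is the institutional rate and the study definition also counts transfused women below 1000 cc.

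- σ = ln(1000/m)/1.9018, where 1.9018 = z(0.9714).
- The proportional cut is chosen so that P(≥ 1000) = 1.43%: new median = 1000/exp(2.1890·σ).
- Overall mean T = m·exp(σ²/2). With d = ln(500/m)/σ, the share measured is p = 1−Φ(d), the part of T from women above 500 is U = T·[1−Φ(d−σ)], and the mean among measured women is U/p.

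| Median, mL | 300 | 350 | 400 |
|---|---|---|---|
| σ | 0.633 | 0.552 | 0.482 |
| Cut in loss | 16.6% | 14.7% | 12.9% |
| Mean loss, all women | 367 → 306 | 408 → 348 | 449 → 391 |
| True difference | 61 | 60 | 58 |
| Share above 500 | 21.0% → 13.7% | 25.9% → 17.5% | 32.2% → 22.7% |
| Mean among measured | 753 → 719 | 728 → 697 | 709 → 681 |
| Difference seen (from unrounded values) | 33 | 30 | 28 |
| Seen / true | 55% | 51% | 48% |

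With a fixed 50 cc cut instead, the measured mean goes 753 → 758, 728 → 730 and 709 → 708. Against a true 50, that is −10%, −4% and +2%.

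**If the rule is loose.** The protocol says only that Hct is not routine at or below 500 cc. If a random fraction f of those women is also measured, the measured mean is (U + f(T−U))/(p + f(1−p)). For the proportional cut, seen/true is:

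| f | m = 300 | m = 350 | m = 400 |
|---|---|---|---|
| 2% | 87% | 73% | 63% |
| 5% | 116% | 95% | 80% |
| 10% | 140% | 117% | 98% |
| 20% | 149% | 131% | 115% |

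The ratio passes 100% at f = 3.1%, 5.8% and 10.9%. The documents do not give f.

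**Modes pooled.** Take 30% cesareans (assumed), all measured, with mean cesarean loss 750 mL (assumed), m = 350 and the strict rule. The cesarean share of measured women before TXA is 0.30/(0.30 + 0.70·0.259) = 0.623, and the pooled mean is 0.623·750 + 0.377·728 = 741.6.

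- Proportional cut of 14.7% in both modes: the share becomes 0.710, and the mean 0.710·640 + 0.290·697 = 656.7. Seen 84.9; true 0.30·110 + 0.70·59.8 = 74.8; ratio 1.13.
- Fixed 50 cc cut in both modes: 20.6% of vaginal births exceed 500, so the share becomes 0.675, and the mean 0.675·700 + 0.325·729.5 = 709.6. Seen 32.0; true 50; ratio 0.64.

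Over the three medians and mean cesarean losses of 600-900 mL, the proportional cut gives ratios of 0.93-1.34.

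**A second model.** A simulation of Hct itself assumed median vaginal loss 250-350 cc, log-SD 0.4-0.7, a relative Hct fall of 1.5% per 100 cc with noise SD 6, and multiplicative error in estimated blood loss (EBL). In vaginal births with error log-SD 0-0.25, 32-76% of the effect of a 20% cut was seen, and −13% to 4% of a 50 cc cut. With error log-SD 0.5-0.8, the 20% cut showed 95-110% and the 50 cc cut at most 54%. Pooled, with 25% cesareans, median cesarean loss 700 cc and error log-SD 0.25, ratios were 0.46-0.72 for a fixed-volume cut and 0.99-1.49 for a proportional one.

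**The case against.** The strongest reply is that the protocol discloses the selective availability, that Hct is one of many secondary outcomes, and that no direction of bias can be asserted. Most of this stands. A reader might infer that the plan will simply hide a TXA effect. The documents do not support that, because they leave open how many women at or below 500 cc are measured, how accurate EBL is, how TXA shifts the loss, and whether modes are pooled. Supplement B has nurses report abnormal vital signs, dizziness and heavier lochia, so clinically prompted draws below the threshold are plausible (an inference).

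A reader might also set the relative reductions side by side (4.4/4.2/4.0% among measured women against 16.6/14.7/12.9% overall) and conclude that only 27-31% of the effect is seen. Those percentages have different denominators. A t-test compares mean differences, for which the figure is 48-55%.

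It can also be said that barring a vaginal-birth test is partly a matter of preference, since reporting by mode with counts would already disclose the problem. That is fair. But disclosure alone does not tell the analyst what to compare. The protocol already uses mode-specific denominators for surgical intervention and reoperation, and Hct lacks one.

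**Conclusion.** The concern holds as a selection problem of unknown direction. Confidence is high that measurement after vaginal birth depends on a post-treatment event and that no analysis sentence handles it. Confidence is low on which way the result is pushed. Bias toward hiding an effect is the expected direction only within vaginal births, under a strictly applied threshold and reasonably accurate EBL. Looser measurement or pooling with cesareans can exaggerate the effect instead. All sizes rest on the assumed blood-loss distributions, on mL as a proxy in the main model, and on the assumed cesarean share. The effect is confined to this secondary outcome. It should be corrected, but it does not threaten the trial's main question.

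**What to change.** Add to the hematocrit definition under Secondary outcomes:

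> Percent Hct decrease is analysed separately by mode of delivery. The inferential comparison is limited to cesarean deliveries in both the study and historic groups. For vaginal deliveries, Hct change is reported descriptively, with the number measured out of the number delivered in each period, and is not interpreted as a test of TXA effect.

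On the Supplement A timing, mode of delivery is settled before TXA starts, so separating by mode introduces no new selection by treatment. The Primary Outcome section describes TXA as given before delivery, and the two passages must be reconciled.

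The change needs no extra blood draws and no new variables. It gives up an inferential Hct result for vaginal births. It also costs precision: if a share c of 20-40% of the 890 deliver by cesarean (assumed), 178-356 women remain. The standard error relative to using all measured women, assuming equal variance, is √((c + (1−c)p)/c). That is 1.24-1.51 at c = 0.2 and 1.10-1.22 at c = 0.4, for p between 13.7% and 32.2%. Confounding from the historical control remains.

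### Planned cesarean hysterectomy is excluded from the study, but nothing removes it from the historic benchmark for the hysterectomy rate, which would bias that comparison toward TXA

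*Combined protocol and SAP*

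**What the plan says.** Four parts of the document bear on this.

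- Subject Population, exclusion b, removes "Planned cesarean hysterectomy".
- Secondary outcomes, Rates of hysterectomy, defines the outcome as "the number of patients requiring hysterectomy divided by the total number of deliveries". Nothing limits it to unplanned procedures or to procedures done for bleeding. Related outcomes in the same list are limited: ICU admission is "admission to the intensive care unit secondary to excessive blood loss divided by the total number of deliveries", and reoperation counts returns to theatre "for the purposes of controlling excessive blood loss divided by the total number of cesarean deliveries". Surgical intervention after vaginal delivery carries the same blood-loss limit.
- Study Procedures, Data Analysis, item 3, states "The secondary outcomes will also be tested against institutional rates". Under Data collection, item 5, the source is described thus: "Chart review will be performed to estimate institutional rates of the secondary outcomes in the 12 months preceding the initiation of the protocol". Data Analysis item 3 then adds "Institutional rates will be estimated by record sampling done at the time of data collection". Neither passage says which records are eligible.
- Research Design, item c, reads "Methods: One Arm", so no concurrent control group would share the same exclusions.

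**The concern.** Most exclusions remove women whose risk of an outcome may differ from that of the women who remain. This one removes the outcome event itself: every planned cesarean hysterectomy is a hysterectomy. If such cases are in the historic numerator, the two rates count different things whatever TXA does, and the direction of the error is known. Adjusting for the listed patient variables cannot correct it, because one cohort cannot have the event.

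Two things are at stake. The estimated effect on hysterectomy would be too favourable to TXA. And a benchmark that is too high raises the number of events needed before an excess of unplanned hysterectomy stands out. The same historic women could also raise the transfusion and ICU comparators, by an amount the documents do not allow one to size.

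**Working it through.** **The plan's own figure.** The only sample size given is 890, for postpartum hemorrhage at 2.86% reduced by half to 1.43%. A one-sample test of a proportion reproduces it, assuming two-sided 5% and 80% power (neither is stated):

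n = [(1.96·√(0.0286·0.9714) + 0.8416·√(0.0143·0.9857)) / 0.0143]² = 890.

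One-sided 5% with 90% power gives 889, so the assumptions cannot be pinned down. Either way the institutional rate is treated as a known constant. No hysterectomy rate or planned share is given, so every rate below is an assumption.

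**Bias in the estimate.** Let p be the historic hysterectomy rate over all deliveries and s the share that was planned. With an inactive drug, the rate expected among eligible women is p(1−s)/(1−ps), so the apparent risk ratio is (1−s)/(1−ps), or about 1−s when p is small.

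Example: for p = 0.002 and s = 0.5, the eligible rate is 0.001/0.999 = 0.001001 and the risk ratio 0.50. In 890 women the benchmark predicts 890 × 0.002 = 1.78 hysterectomies, against 0.89 expected with no drug effect. Shares of 25%, 50% and 67% give risk ratios of about 0.75, 0.50 and 0.33, almost regardless of p. With the planned cases removed the ratio is 1.00.

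**Detection of harm.** Assume an unplanned rate of 0.1% and a true tripling to 0.3%. With n = 890, find the smallest count c for which P(X ≥ c) ≤ 0.025 at the benchmark rate, then compute P(X ≥ c) at 0.3%.

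| Planned cases add | Benchmark | Planned share | Events needed | Chance of flagging the tripling |
|---|---|---|---|---|
| 0 | 0.10% | 0% | 4 | 28% |
| 0.05 points | 0.15% | 33% | 5 | 13% |
| 0.1 points | 0.20% | 50% | 6 | 5% |
| 0.2 points | 0.30% | 67% | 7 | 2% |

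The plan names the chi-square test. Uncorrected and in one-sample form, it gives 50%, 28%, 13% and 5%. But at the matched benchmark only 0.89 events are expected, and that test rejects upward at 3 events with an upper-tail error of 6.1% rather than 2.5%. The exact figures are the fairer ones. The relative loss is similar under either test.

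**False significance for benefit.** The most favourable possible result is 0 events in 890. Against a fixed benchmark it is significant in the lower 2.5% tail only if (1−p)^890 ≤ 0.025, that is p ≥ 1 − 0.025^(1/890) = 0.41%. The chi-square equivalent is p > 3.841/(890 + 3.841) = 0.43%. Below that, a falsely significant benefit cannot occur. Above it, with s = 50%, the exact chance is 10.7% at a benchmark of 0.5% and 34.6% at 1%.

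If the benchmark is instead treated as a sample, the cut-off is not absolute. With an assumed 3,000 historic deliveries and s = 50%, a two-sample chi-square test gives 0.4%, 11.0% and 24.3% at 0.2%, 0.5% and 1%. With no planned cases in the benchmark it gives 0.15%, 1.6% and 1.7%.

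**The case against.** The strongest reply is that the mismatch is inferred from silence. The plan never says that the institutional records are unrestricted. It does not show that any planned cesarean hysterectomy took place in those 12 months, and record sampling might miss a rare case. If none is drawn, this bias is zero. This stands, and it makes the point conditional.

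The outcome wording could also be read as need arising at delivery, since the list uses the same verb for transfusion and ICU need. That is possible, but related outcomes state a blood-loss limit and this one does not. A chart reviewer following the text would have no instruction to leave planned cases out.

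Third, 890 women carry little information on so rare an event: even with a matched benchmark, a tripling would usually be missed. That is true and limits the weight of the point, but it does not justify a comparator that loses more.

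Fourth, the plan stratifies outcomes by hemorrhage risk and puts suspected accreta or percreta in the high-risk group. Similar stratification of the benchmark would confine planned cases with those indications to one stratum. The plan does not say the benchmark will be stratified, and the mismatch would remain within that stratum.

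Finally, none of the exclusions is stated to apply to the historic records, so filtering on this one alone would be incomplete. That is fair, and the fix allows for it.

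**Conclusion.** The mismatch is real on the natural reading of the plan and should be closed. Planned cesarean hysterectomies in the historic records would bias the comparison toward TXA by about their share of historic hysterectomies and would weaken detection of harm as tabulated. The direction follows from the definitions; the size rests on assumed rates and shares.

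A reader might infer more: that the benchmark certainly contains these cases, or that the study will show a false TXA benefit. The documents support neither. They give no hysterectomy count, planned share or record-selection rule. Against a fixed benchmark below about 0.4%, no result from 890 women could be a significant benefit. At low rates the damage is to the estimate and to harm detection, not to the error rate on the benefit side.

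This concerns one rare secondary outcome. It leaves the primary outcome definition and the 890 as they are.

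**What to change.** Define the outcome in both cohorts as unplanned hysterectomy divided by deliveries without a planned cesarean hysterectomy. In the 12-month chart review, remove deliveries with a planned cesarean hysterectomy from numerator and denominator, preferably by applying every trial exclusion that the records can identify. State how planned is to be recognised in the chart. Use the same restricted historic set for the ICU and transfusion comparators. Reconcile the chart-review and record-sampling descriptions of the benchmark in the same edit.

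Fix these rules before the review starts; a filter chosen after the rates are seen would not be credible.

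The cost is a clause in the outcome definition and one extra filter in a review already planned, with no additional patients or procedures. The downside for the sponsor is a lower, less favourable benchmark if planned cases are found.
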